## **ANALYSIS SET AND STUDY POPULATIONS**

The primary outcome of the study will be analyzed according to the intention-to-treat (ITT) principle. The full analysis set of data will be derived from the set of all randomized participants. Participants allocated to a treatment group (i.e., LC or CTL) will be analyzed as members of that group irrespective of their compliance to the planned treatment. Those with both missing baseline and follow-up value will not be included in the analysis, which is unbiased under a plausible missing at random assumption. All outliers that are within the realm of biological plausibility will be included in the analysis and only obvious data errors (e.g., resulting from technical issues) will be excluded. If there are statistical outliers within the realm of biological plausibility ( $>2.2 \times \text{IQR}$  from mean), the data will be presented with and without the outliers included for completeness.

## **ANALYSIS OBJECTIVES, OUTCOMES, AND STATISTICAL METHODS**

All data were collected longitudinally. Statistical analysis will be performed blinded to participant allocation after the last participant has completed the trial.

**Primary endpoint:** The prespecified primary outcome for this trial will be a comparison of the change in HbA1c (in the standard percentage units) from baseline to 12 weeks between the dietary intervention groups.

The analysis of the primary outcome is based on a superiority approach (i.e., we expect that the LC intervention will be superior in leading to decreased HbA1c compared to the CTL intervention). Data will be analyzed by constrained longitudinal data analysis (cLDA) via a linear mixed model with fixed effects for timepoint (baseline and week 12), the interaction between timepoint and dietary intervention group, and stratified allocation factors (sex) as well as random effects for participants to account for the correlation of repeated measures within participants.

The cLDA approach constrains the baseline means to be equal between the treatment groups, which is a reasonable assumption in the context of a randomized controlled trial. If a participant does not have any HbA1c recordings in the end of the trial, only the baseline value of that participant will be included in the model and no post-intervention value for that participant will be included. No missing data will be imputed as per contemporary guidelines. Model specification will be assessed visually using normal probability plots and residuals vs. fitted values plots. Models will be run using log-transformed outcome variables when departure from model assumptions is observed.

**Secondary outcome measures:** To supplement the primary outcome of A1c, continuous glucose monitors (CGMs) will be worn by participants during the first and last 14 days of the intervention (i.e., both timepoints of CGM will be collected while participants are consuming their allocated breakfast). Changes in CGM variables (fasting glucose, mean glucose, maximum glucose, minimum glucose, 24-h area under the curve, incremental area under the curve, MAGE, SD, time below 3.9 mmol/L, time above 10mmol/L , time in range (3.9-10 mmol/l); 2-hour post-meal: incremental area under the curve, mean glucose, maximum glucose and SD will be calculated for each 14 day period. CGM data will be analyzed using a linear mixed model that will include fixed effects for timepoint (First 14 days vs Last 14 days), group (LC vs. CTL), their interaction, and stratified allocation factors (sex) and random effects for participants. In this analyses the main effect of group will be most important to identify an overall effect of the intervention on glycemic control variables.

Continuous secondary outcomes will be analyzed similarly to the primary outcome using a constrained baseline longitudinal data analysis linear mixed model (with all relevant follow-up timepoints included as a fixed factor in the model). Secondary outcomes include:

1. Changes in self-reported satiety and fullness assessed with a 100 mm visual analogue scale (VAS) on satiety and fullness at baseline, midpoint and 12 weeks, which were based on those validated by Flint et al. (1).
2. Changes in self-reported dietary intake (total kilocalories, grams of carbohydrates and percent of total calories, grams of protein and percent of total calories and grams of fat

and percent of total calories, egg consumption) assessed via self-report (3-day dietary records) at baseline, midpoint and 12 weeks.

3. Changes in self-reported body weight and body mass index from baseline to 12 weeks.
4. Changes in blood markers (fasting insulin, high-sensitivity C-reactive protein, triglycerides, total cholesterol, HDL, LDL and VLDL) from baseline to 12 weeks.
5. Changes in carotenoid levels (lutein and zeaxanthin) from baseline to 12 weeks.
6. Changes in cognitive function from baseline to midpoint and 12 weeks.

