Recruitment was originally closed on November 2021 after  $n = 92$  participants were randomized; however, based on the nature of the remote trial and participants dropping out after randomization, only 78 participants had baseline A1c data. Unexpectedly, 4/35 participants who completed the study in one group failed to obtain follow-up A1c and 2/33 in the other group failed to obtain follow-up A1c, resulting in complete data on  $n = 31$  per group. Reasons included the impact of COVID-19 and winter holidays coinciding with study conclusion or were not reported by the participants. A blinded analysis of the primary outcome by an independent statistician not involved in any other aspect of the trial was completed on January 16, 2022. After consultation with the statistician, the research team made the decision to re-open recruitment in order to obtain sufficient sample size based on the original calculations. Using an updated estimation of loss to follow up (62 complete data out of 92 randomized = 33%), we aimed to recruit an additional 10-12 participants in order to maximize the chances of having  $n = 34$  per group for final analyses.

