## HANDLING OF MISSING DATA AND OTHER DATA CONVENTIONS

No statistical imputations will replace missing data for the outcome measures (*data as observed*). However, the constrained baseline longitudinal data analysis – in a linear mixed model with restricted maximum likelihood – is a principled approach to addressing missing outcome data, including the baseline value of the continuous outcome measure. The model permits the inclusion of all participants in the analysis with either a baseline or a follow-up value. Thus, missing data will not be imputed for the ITT analyses. If a blood marker value is below the detection limit, we will explore the results following imputation of the value as limit of detection (LOD) divided by the square root of 2 (6).

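### The primary cLDA has no sex-by-timepoint term, so it assumes a constant sex difference in HbA1c; adding the term is a minor, cheap safeguard against sex-related loss at week 12

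*SAP*

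**What the plan says.** The SAP (Analysis Objectives, Outcomes, and Statistical Methods, primary endpoint) fits a constrained longitudinal model to baseline and week-12 HbA1c with "fixed effects for timepoint (baseline and week 12), the interaction between timepoint and dietary intervention group, and stratified allocation factors (sex") and "random effects for participants to account for the correlation of repeated measures within participants". The only interaction named is timepoint by group, so on the natural reading sex is a main effect.

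On baseline and missing values:
- Baseline: "The cLDA approach constrains the baseline means to be equal between the treatment groups".
- A participant without a week-12 result: "only the baseline value of that participant will be included in the model and no post-intervention value for that participant will be included".
- Leaving out participants with neither value is described as an analysis "which is unbiased under a plausible missing at random assumption" (Analysis Set and Study Populations).
- The section on missing data says that the model "is a principled approach to addressing missing outcome data".

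Continuous secondary outcomes other than CGM are to be "analyzed similarly to the primary outcome using a constrained baseline longitudinal data analysis linear mixed model", so they take the same form.

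No other section supplies the missing term. The protocol's Statistical Analysis section says only that age and sex are in the model. The SAP's sensitivity analyses cover site, adherence and egg intake.

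**The concern.** With baseline in the outcome vector, a sex main effect forces the male-female difference to be equal at both visits. The diet effect is the difference between groups at week 12 given baseline. Sex can still affect that contrast through a male-female difference in change, and the model has no term for it. An ANCOVA with sex as a covariate would adjust the week-12 value for sex directly; in a cLDA the equivalent needs sex by timepoint.

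Stratified allocation balances sex at randomisation, but not among those who supply a week-12 result. Loss that depends only on sex and arm is missing at random, since both are observed. The likelihood analysis is protected against such loss only if its mean model is right. What is at stake is a small shift in the primary estimate that a reader would assume had been removed, because sex is in the model.

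**Working it through.** **1. The plan's loss figure, and the one that applies here.** The SAP's sample-size adjustment gives "62 complete data out of 92 randomized = 33" per cent: (92 − 62)/92 = 32.6%. That denominator includes 92 − 78 = 14 participants with no baseline HbA1c. Among those with a baseline value, 78 − 62 = 16 lack the pair, and 16/78 = 20.5%. Complete pairs are 35 − 4 = 31 and 33 − 2 = 31, so they are equal by arm. No split by sex is given.

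**2. Inputs.**
- Correlation r: 0.5 from the SAP's sample-size section; 0.8 is added as an assumption.
- SD: 1.0 point, an assumption. It follows if the SAP's d = 0.46 was derived from the 0.46-point reduction (0.46/0.46).
- Sex effect: g0 at baseline and g1 at week 12, with g1 − g0 = 0.3. Assumption; the documents give none.
- Numbers: 39 with a baseline value per arm, half of them women, and 8 lost per arm (39 − 8 = 31). The equal split and the sex pattern are assumptions.
- No true diet effect.

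**3. Formula.** Two visits with a participant random intercept give compound symmetry. With all baselines present and balanced by sex, the expected generalised least squares contrast is

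bias = D × [(g1 − γ) − r(g0 − γ)],

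where D is the difference between arms in the share of women observed at week 12, and γ is the single sex coefficient the model fits.

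- If g0 = g1, then γ = g0 and the bias is 0 for any D.
- If they differ, γ falls near their midpoint, and bias ≈ (1 + r)/2 × (g1 − g0) × D.
- With sex by timepoint, each visit has its own sex coefficient, both brackets vanish and the bias is 0.

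**4. Example.** Six of one sex and two of the other are lost in one arm, and the reverse in the other arm. Observed cells are 17.5 and 13.5 of 31, so D = 4/31 = 0.129. With g0 = 0, g1 = 0.3 and r = 0.5, γ = 0.124, and the bias is 0.129 × [0.176 + 0.062] = 0.031. The approximation gives 0.75 × 0.3 × 0.129 = 0.029.

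**5. Results** (g0 = 0, g1 = 0.3; each pair is r = 0.5, then r = 0.8).

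| Week-12 pattern, reversed between arms | D | Bias as written | SE as written | Bias/SE | SE with sex by timepoint |
|---|---|---|---|---|---|
| 39 per arm, lose 5 + 3 | 0.065 | 0.015, 0.018 | 0.220, 0.152 | 0.07, 0.12 | 0.220, 0.153 |
| 39 per arm, lose 6 + 2 | 0.129 | 0.031, 0.036 | 0.220, 0.153 | 0.14, 0.23 | 0.222, 0.154 |
| 40 per arm, 80%/60% observed | 0.143 | 0.035, 0.040 | 0.232, 0.161 | 0.15, 0.25 | 0.234, 0.162 |
| 40 per arm, 90%/60% observed | 0.200 | 0.048, 0.056 | 0.225, 0.155 | 0.22, 0.36 | 0.228, 0.158 |

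The bias with sex by timepoint is 0.000 in every row. In the last row, a model with no sex term would be off by 0.3 × 0.2 = 0.060, so the planned main effect removes only 0.012 (19%) or 0.004 (7%) of it.

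**6. When nothing happens.**
- Constant sex effect (g0 = g1 = 0.3): the bias is 0.000 under every loss pattern tried, including 60%/6% loss crossed by sex and arm. There a model without sex would be off by 0.060.
- Loss by sex alone or by arm alone: the bias is 0.000.
- Additive sex and arm loss (60/80% v 75/95% retained): 0.003.

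**7. Inference.** A REML simulation with 46 per arm and loss of 30%/12% crossed gave type I error of 6.2% as written and 5.7% with the interaction, with Monte Carlo error of about 0.4 to 0.5 points.

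**The case against.** A reader might infer that the planned contrast is hardly adjusted for sex, and that it is biased whenever week-12 loss differs by sex and arm. The documents do not support that. With a constant sex effect the SAP's model is correctly specified and removes all of the imbalance (step 6). Differential loss alone is not enough; sex must also predict change.

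Nor do the documents show either condition. They give no sex effect on HbA1c or its change, and no loss by sex. Complete pairs are 31 in each arm. The reasons reported for missing follow-up HbA1c (COVID-19, winter holidays, or none given) do not suggest opposite sex patterns in the two arms. The assumed 0.3 points is large, about two thirds of the 0.46-point reduction behind the sample size, and the reversed pattern is close to a worst case. Citing a third of pairs as incomplete would also overstate the relevant loss, which is 20.5%.

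All of this stands, and it makes the point minor. Equal totals by arm do not settle the matter, however: the first two rows of the table keep exactly 31 pairs per arm and still show bias.

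A last objection is that zero bias after the fix is guaranteed because the data were generated without a sex-by-diet interaction. That is also right. If the diet effect differs by 0.3 points between the sexes and 90%/60% are observed by sex in both arms, both models estimate 0.6 × 0.3 = 0.18 against a true average of 0.15. The added term does not help there.

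**Conclusion.** The point holds as a minor specification improvement. The SAP's missing-data argument carries an unstated assumption that the male-female HbA1c difference is the same at baseline and week 12. If that fails, and loss also shifts the sex mix differently by arm, most of the imbalance remains in the primary estimate.

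At the reported loss, the bias is about 0.015 to 0.036 points, or 0.07 to 0.23 standard errors. With 90%/60% crossed retention it is 0.048 to 0.056 points. These figures rest on an SD of 1%, a 0.3-point sex difference in change, r of 0.5 to 0.8 and reversed loss patterns, and bias scales in proportion to the sex difference. Such a shift would rarely change the conclusion by itself. Without differential loss the added term gains essentially nothing. The loss counts predate the reopening of recruitment, and the documents do not give the final ones.

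**What to change.** In the SAP's primary endpoint paragraph, replace the single sex term with sex and sex-by-timepoint. Make the same change in the constrained-baseline models for the secondary outcomes. The treatment contrast remains the timepoint-by-group term at week 12.

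The SAP describes the trial as completed in June 2022. If the primary analysis has already been run, keep it as specified and report the extended model as a labelled addition to the sensitivity analyses. Tabulating week-12 HbA1c availability by arm and sex would show whether the loss condition arises.

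The cost is a few words and one degree of freedom per follow-up visit. The standard error rises by about 0 to 2% in the tabulated cases. Under the extreme 60%/6% crossed loss it goes from 0.224 to 0.241, about 8%. The change does not address a diet effect that differs by sex.

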## Research Method

Eighty-two (N=82) individuals between University of British Columbia and University of Wollongong, Australia with physician diagnosed T2D (HbA1c < 8.5%), between the ages of 20-79 years, with a BMI above 25 kg/m^2 will be recruited through online social media and newspaper advertising. REACH BC and Trialfacts will assist with recruitment. REACH BC is an initiative of BC's health authorities and partner universities bridging the gap between the public and researchers. Trialfacts combines extensive marketing and advertising expertise with in-depth clinical trial experience to create effective marketing solutions. We have a partnership with the Kelowna Diabetes Program to assist recruiting from >6500 well-monitored T2D patients in our region.

**Inclusion criteria** will be: i) physician-diagnosed T2D of  $\geq 1$  year; ii) current HbA1c of <8.5%; iii) BMI: higher than 25kg/m^2; iv) blood pressure of <160/99 mm Hg assessed according to guidelines; v) non-smoking; vi) not on hormone replacement therapy, corticosteroids, or anti-inflammatory medications; and vii) 20–79 years old. **Exclusion criteria will include:** i) Use of exogenous insulin; ii) taking more than 2 glucose lowering medications; iii) ongoing medical treatment for diseases such as cancer, auto-immune or inflammatory disease, liver or kidney disorders; iv) allergy, intolerance or aversion to eggs or any other dietary restrictions (e.g., vegan, breakfast skipping) that will prevent them from following the standardized study diets; v) being unable to follow remote guidance by internet or smartphone; vi) being unable to follow the controlled diet instructions;.

Based on our previous studies ~55% of males and ~70% of females with T2D who volunteer will meet these eligibility criteria so we anticipate no recruitment issues. We will allow statins and anti-hypertensive medications if on a stable dose for 3 months because the majority of T2D patients are on at least one of these medications; excluding them would leave a small pool for recruitment and limit the generalizability of our findings.

A 3-month parallel-group randomized controlled trial is proposed. Eligible participants will be randomized to either the Low-carb High-fat breakfast (LCHF, n=41) or a low-fat “standard care” control breakfast (CTL, n=41), to be consumed daily for a period of 3 months.

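### The primary HbA1c model names only participant random effects; the default fit assumes equal variance at baseline and week 12, so its error rate depends on an unstated SD ratio

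*SAP*

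**What the plan says.** Under the primary endpoint (SAP, Analysis Objectives, Outcomes, and Statistical Methods), change in HbA1c is analysed by cLDA in a linear mixed model. The fixed effects are timepoint (baseline, week 12), timepoint by group, and sex, "as well as random effects for participants to account for the correlation of repeated measures within participants". Baseline means are constrained equal across arms. The section on missing data adds the estimation method, "in a linear mixed model with restricted maximum likelihood". Neither document names a residual covariance, visit-specific variances, robust standard errors or a degrees-of-freedom method. The protocol's Statistical Analysis section says only that a linear mixed effects model will be used.

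The model check is visual (normal probability plots and residuals against fitted values), with one remedy: "Models will be run using log-transformed outcome variables when departure from model assumptions is observed". For the other endpoints, "Continuous secondary outcomes will be analyzed similarly to the primary outcome".

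Two further facts matter. The protocol's inclusion criteria require "current HbA1c of <8.5" per cent at entry, and nothing caps HbA1c at week 12. The SAP's sample size section records that "only 78 participants had baseline A1c data" and gives "62 complete data out of 92 randomized" at the January 2022 look.

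**The concern.** With two visits, a participant random slope plus a free residual variance cannot be identified. The natural implementation of the SAP's sentence is therefore a random intercept with independent, equal-variance residuals, which forces the same HbA1c variance at both visits.

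That assumption matters because of the baseline constraint. In an unconstrained model with complete pairs, the group-by-time interaction is the two-sample t-test on change scores, whose standard error does not depend on the two visit SDs being equal. The constrained model instead adjusts the week-12 difference for the baseline difference, with a slope and a residual variance both taken from the assumed covariance. If the week-12 SD exceeds the baseline SD, the reported standard error of the treatment contrast is too small and false positives exceed 5%. If it is smaller, the test is conservative and power is lost. This model supplies the primary p-value and confidence interval.

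Some widening is plausible, because the entry cap truncates baseline HbA1c and week 12 is free to spread.

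**Working it through.** **The plan's own figure.** For the repeated-measures ANOVA with f = 0.2, r = 0.5 and two visits, the noncentrality is f²·N·m/(1−r) = 0.04 × 68 × 2/0.5 = 10.88 on (1, 66) df. Power is 0.9015 at N = 68 and 0.8926 at N = 66, so N = 68 reproduces. That calculation concerns the unconstrained interaction and is not affected by this point.

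**Inputs.**
- From the SAP's sample size section: 78 with baseline HbA1c and 62 complete (31 per arm).
- Derived: 78 − 62 = 16 baseline-only, assuming all 62 are among the 78. They are split 8 and 8 by assumption.
- Assumed, because the documents give no HbA1c SD: k from 0.8 to 1.5 and baseline-to-week-12 correlation r = 0.7. Baseline SD is set to 1.
- The test is taken as two-sided 5%; the SAP does not state sidedness.

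**Closed form.** Let the random-intercept model settle on common variance v and correlation ρ. These minimise the expected minus log-likelihood under the true covariance:

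31·[ln(v²(1−ρ²)) + (1 + k² − 2ρrk)/(v(1−ρ²))] + 8·[ln v + 1/v]

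The treatment estimate is the difference between arms in (week-12 mean − ρ × baseline mean) among completers, because the common baseline mean cancels. With n = 31 per arm:

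- model variance = 2v(1−ρ²)/n
- true variance = 2(k² + ρ² − 2ρrk)/n
- actual type I error = P(|Z| > 1.96 × model SE/true SE)

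Worked case, k = 1.25: v = 1.237 and ρ = 0.674.
- Model SE = √(2 × 1.237 × (1 − 0.674²)/31) = 0.209.
- True SE = √(2 × (1.5625 + 0.454 − 1.180)/31) = 0.232.
- The unrounded ratio is 0.898, and P(|Z| > 1.96 × 0.898) = 0.079.

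| k | Type I error, 31 complete + 8 baseline-only per arm |
|---|---|
| 0.8 | 2.6% |
| 0.9 | 3.8% |
| 1.0 | 5.0% |
| 1.1 | 6.2% |
| 1.25 | 7.9% |
| 1.5 | 10.2% |

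Taking r from 0.5 to 0.8 moves these by at most about 0.1 point. With 34 complete and 9 baseline-only per arm, the results at k = 0.8, 1.1, 1.25 and 1.5 are again 2.6%, 6.2%, 7.9% and 10.2%. With complete data only, the ratio of true to model variance is 2k²/(1+k²) whatever r is, which gives 6.1% at k = 1.1 and 9.6% at k = 1.5.

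**REML simulation under the null** (3000 trials per cell, Monte Carlo SE about 0.4 points, 39 baseline and 31 complete per arm, sex in the model, r = 0.7, t-test on completers − 2 df):

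| k | Random intercept | Unstructured 2x2 |
|---|---|---|
| 0.8 | 3.3% | 5.5% |
| 0.9 | 4.0% | 5.6% |
| 1.0 | 5.1% | 5.5% |
| 1.1 | 6.7% | 5.7% |
| 1.2 | 6.9% | 5.3% |
| 1.3 | 8.1% | 5.4% |
| 1.5 | 10.5% | 5.5% |

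Across all settings simulated this way, including r = 0.5 and 43/34 per arm, the unstructured fit lies between 5.0% and 6.4% with no trend in k. The small excess over 5% is a degrees-of-freedom matter.

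**Power at k = 0.8, r = 0.7.** The unstructured SE is √(2 × 0.64 × 0.51/31) = 0.145. An effect with 80% power is (1.96 + 0.842) × 0.1451 = 0.407. The random-intercept model SE is 0.169 and its true SE 0.149, so power is P(Z > (1.96 × 0.1690 − 0.4065)/0.1489) = 69%. Starting from the planned 90%, the same steps give 82%.

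**Entry cap alone.** Assume normal HbA1c before the cap, mean 7.0 to 7.5, SD 0.8 to 1.2, visit correlation 0.6 to 0.8, truncated at 8.5 at baseline only. Then k runs from 1.03 to 1.21 and type I error from 5.3% to 7.5%. The middle case (7.25, 1.0, 0.7) gives k = 1.10 and 6.2%.

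**Log transform.** For normal data with baseline mean 7.0, SD 0.7 and k = 1.25, the log-scale k is 1.26 if the mean stays at 7.0 (about 8%) and 1.32 if it falls to 6.7 (8.6%).

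**The case against.** The SAP never says random intercept, compound symmetry or independent residuals. A participant effect can be combined with visit-specific residual variances, and every inflated figure above presumes that it is not. That is fair: equal variance is the default reading, not a stated choice. But the text supports no other structure, and leaving it open lets it be settled after the results are seen.

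The size rests wholly on an assumed k. This stands. The only mechanism in the documents is the entry cap, which supports roughly 5% to 7.5%; k = 1.5 is not motivated by anything in them. At k = 1.1 the proposed fix gains about one percentage point (6.7% against 5.7% simulated). No comparable mechanism is established for k below 1, so the power loss is the weaker half. The protocol does allow a baseline HbA1c up to a month old but wants the final one within a week of study end, which could add baseline spread and offset part of the cap's effect by an unknown amount.

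The planned plots and log transform are a partial safeguard. In the entry-cap scenarios, logging brings the top of the range down to about 7.0%. It does not repair a general widening when the mean is flat or falling, and no rule addresses unequal variance between visits.

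For secondary outcomes the structure is equally unstated, but no size can be given, and the entry-cap argument applies to HbA1c only. The CGM outcomes use a separate, unconstrained model that this point does not reach.

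**Conclusion.** The point holds as a gap in the primary analysis that should be closed. Under the natural fit of the stated model, the week-12 standard error is wrong whenever the two HbA1c SDs differ, and the log-transform remedy does not correct that in general. The likely effect is mild: about 5.3% to 7.5% instead of 5% if the entry cap is the only source of unequal variance. About 10% would need k = 1.5. If k were 0.8, the test would run at 2.6%, and power would fall from 80% to about 69%, or from 90% to about 82%. These figures assume the random-intercept reading, a two-sided test, an 8/8 split of baseline-only participants and an unknown k. The planned sample size is not called into question.

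**What to change.** State in the SAP that the cLDA uses an unstructured covariance across visits: 2x2 for HbA1c and other two-visit outcomes, 3x3 for three-visit outcomes. Fit it by REML with Kenward-Roger degrees of freedom, and keep the random-intercept fit as a sensitivity analysis. The SAP records "A blinded analysis of the primary outcome by an independent statistician" in January 2022 and describes the study as completed in June 2022. The change should therefore carry a date, and both fits should be reported.

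The cost is one extra variance parameter for two-visit outcomes, a dated SAP revision and a second reported fit. At k = 1, where the random intercept is correct, the simulated spread of the treatment estimate was 0.126 with the random intercept and 0.127 with the unstructured fit (0.127/0.126 = 1.008), a loss of under 1%.
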